13.1.1.2. Serious Adverse Event

An AE is considered “serious” if, in the view of either the Investigator or Sponsor, it results in any of the following outcomes:

- Death
- Is immediately life threatening
- Requires in-patient hospitalization or prolongation of existing hospitalization
- Results in persistent or significant disability or incapacity
- Results in a congenital abnormality or birth defect
- Is an important medical event that may jeopardize the patient or may require medical intervention to prevent one of the outcomes listed above.

Events **not** considered to be SAEs are hospitalizations for:

- Routine monitoring of the studied indication and not associated with any deterioration in condition or AE;
- Elective treatment for a pre-existing condition that did not worsen;
- Respite care or observation when there is no AE associated with the hospitalization.

13.1.1.3. Treatment-Emergent Adverse Event

A treatment-emergent AE (TEAE) is any event not present before the initiation of the investigational product or any event already present that worsens in either intensity or frequency following exposure to the investigational product.

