8.4.1. Other Reasons for Discontinuation of Study or Investigational Product

The following events are considered appropriate reasons for a patient to discontinue investigational product; however, these patients are expected to continue in the study until study termination (or at the discretion of the Sponsor):

- Patient begins treatment with commercially available OCA.
- The Investigator or Sponsor considers that it is advisable or in the best interest of the patient.

- The occurrence of clinical or laboratory AEs considered by the Investigator to be clinically important safety concerns and related to study drug.
- Withdrawal of consent
 - Consent may be fully withdrawn (in which case the patient discontinues both investigational product and study visits and procedures).
 - Consent may be modified to discontinue study visits but allow semi-annual telephone contact.
 - Consent may be modified to discontinue study visits or semi-annual telephone contact but allow continued access to medical records to assess for suspected major adverse cardiovascular events (MACE) and liver-related clinical events.
 - Early termination procedures should be conducted if the patient withdraws consent (see [Section 9.7.13](#)).

The Investigator is encouraged to contact the Sponsor prior to discontinuing a patient from treatment. The Investigator must notify the Sponsor study monitor by telephone or email as soon as possible if any patient prematurely withdraws from the study.

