9. TREATMENT OF PATIENTS

9.1. Investigational Product Treatment Regimen

The term investigational product refers to either OCA (provided as part of this clinical study) or placebo.

Two treatment groups will be evaluated: OCA and placebo. Investigational product will be administered orally. Each dose will be made up of 1 tablet (ie, one OCA 5 mg tablet or one OCA 10 mg tablet, or matching placebo).

Investigational product will be taken orally with water for the duration of the study. Patients will be instructed to begin dosing on Day 1 and are to take investigational product at approximately the same time on dosing days. Patients must be instructed to swallow the tablet whole; they must not chew, divide, or crush the tablet.

At each study visit where the dose of investigational product is administered at the site, all assessments, except for the post-dose collection of blood samples for the PK assessment, must be completed before administration of investigational product.

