9.2.2. Prohibited Medications

Commercial OCA therapy (if available) is prohibited while on investigational product, and if prescribed during the course of the study, the Investigator should be cognizant of the possibility of double dosing. Patients who initiate with commercial OCA therapy must discontinue investigational product and are expected to continue through the end of the study (see [Section 8.4.1](#)). Fibrin acid derivatives (ie, fibrates such as fenofibrate and bezafibrate) are also prohibited while on investigational product.

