13.1.4. Reporting of Adverse Events and Serious Adverse Events

13.1.4.1. Reporting of Adverse Events

AE data will be collected from the time that signed informed consent is obtained until the patient fully completes her/his study participation.

All AEs, whether believed by the Investigator to be related or unrelated to the investigational product, must be documented in the patient's medical records, in accordance with the Investigator's normal clinical practice and on the AE eCRF. Each AE is to be evaluated for

duration, intensity, frequency, seriousness, outcome, other actions taken, and relationship to the investigational product. Redacted medical record source documentation will be requested for all SAEs and emergency room visits.

In addition, the Investigator should contact the study Medical Monitor upon awareness when any signs or symptoms of hepatic decompensation are observed in any patient.

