13.1.6. Notification of Post-Treatment SAEs for Patients Who Continue in the Study

Post-treatment SAEs that occur in patients who remain in the study after investigational product has been discontinued must be reported to the Sponsor within 24 hours by following the instructions provided in [Section 13.1.4.2](#).

SAEs that occur in patients who discontinue investigational product, initiate treatment with commercially available Ocaliva, and remain in the study must be reported to the Sponsor within 24 hours by following the instructions provided in [Section 13.1.4.2](#).

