15.4. Safety Analyses

Safety analyses will be conducted using the Safety population. Safety data, including AEs, AEs of special interest including pruritus and hepatic safety, vital signs, ECG, and clinical laboratory results will be summarized by treatment group using the Safety Population.

The incidence of TEAEs and SAEs will be tabulated by system organ class (SOC) and preferred term (PT) for each treatment group, and similarly by severity and relationship to treatment.

Laboratory parameters, physical examinations including vital signs, and ECGs will be summarized by treatment group using descriptive statistics at Baseline and at each scheduled post-Baseline visit. The absolute change from baseline will also be summarized.

No inferential comparison with formal statistical hypothesis testing will be performed for safety endpoints.

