15.4.4. Adverse Events of Special Interest

Pruritus: Treatment-emergent pruritus, defined as any PT including “Prur,” will be summarized separately by the MedDRA SOC, treatment group, and PT as a subset of all TEAEs. This summary will be repeated for patients with “new or worsened” pruritus events, as defined as follows:

- Mild, moderate, or severe treatment-emergent pruritus events in patients with no pruritus at Baseline, or
- Worsening of the severity of the Baseline condition in patients with pruritus at Baseline.

Baseline pruritus is defined as the Investigator’s rating of severity as collected on the PBC Disease History eCRF. Patients whose Baseline severity is severe will be counted as worsening if an AE of pruritus with severe is recorded.

An analysis of treatment-emergent pruritus event days per patient years on study will be performed. The days at each severity grade, including the total days of event, the total patient years on study, and the event days per patient year on study at each severity grade, including the total, will be summarized. Each individual patient year on study will be derived as the last known date during the study minus the first dose date plus 1 divided by 365.25 days/year.

In order to explore the relationship between pruritus and the investigational product, the following time-to-event analyses will be performed:

- Time to first onset of treatment-emergent pruritus
 - The time to the start of the first episode will be calculated by date of onset of first episode – date of first dose of investigational product + 1.
 - Patients who never reported an AE of pruritus will be censored at the date of last contact.
- Time to onset of the first moderate or severe treatment-emergent pruritus
 - The time to the start of the first moderate or severe pruritus will be calculated by date of onset of the first moderate or severe pruritus – date of first dose of investigational product +1.

- Patients who never reported a moderate or severe AE of pruritus will be censored at the date of completion or discontinuation.
- Time to onset of the first severe treatment-emergent pruritus
 - The time to the start of the first severe pruritus will be calculated by date of onset of the first severe pruritus – date of first dose of investigational product +1.
 - Patients who never reported a severe AE of pruritus will be censored at the date of completion or discontinuation.

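### The treatment-emergent window has no end and does not stop at commercial OCA, so events and time on commercial OCA in placebo patients would be credited to placebo

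*Protocol*

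**What the plan says.** **Definition.** Section 13.1.1.3 calls treatment-emergent "any event not present before the initiation of the investigational product or any event already present that worsens in either intensity or frequency" after exposure to investigational product. Section 9.1 limits that product to study supply: "The term investigational product refers to either OCA (provided as part of this clinical study) or placebo". Commercial OCA is therefore not investigational product.

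**Switching.** Section 8.4.1 lists this among the reasons to stop investigational product while remaining in the study: "Patient begins treatment with commercially available OCA". Section 9.2.2 agrees: "Patients who initiate with commercial OCA therapy must discontinue investigational product and are expected to continue through the end of the study". Table 6, footnote b, places such patients under treatment discontinuation, where those with active consent keep the regular visit schedule.

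**Collection.** Section 13.1.4.1: "AE data will be collected from the time that signed informed consent is obtained until the patient fully completes her/his study participation". Section 13.1.6 foresees the case directly: "SAEs that occur in patients who discontinue investigational product, initiate treatment with commercially available Ocaliva, and remain in the study must be reported".

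**Summaries.** Section 15.4: "The incidence of TEAEs and SAEs will be tabulated by system organ class (SOC) and preferred term (PT) for each treatment group". The only groups are OCA and placebo (9.1, 9.4.1). The Safety Population (15.1) needs one dose and carries no as-randomized or as-treated rule.

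**Person-time and censoring.** For both pruritus and fatigue, 15.4.4 states: "Each individual patient year on study will be derived as the last known date during the study minus the first dose date plus 1". Time to first pruritus and all three fatigue endpoints are censored at last contact. Moderate-or-severe pruritus and severe pruritus are censored at completion or discontinuation, without saying whether of study or of drug.

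**The concern.** Safety and tolerability against placebo is a primary objective (6.1), and 5.4.4 calls the placebo control critical for it. A placebo patient who starts commercial OCA is exposed to the drug under test, yet nothing in the safety section separates that exposure from placebo exposure. The events most affected are the ones the trial is there to compare: pruritus, named in 5.6 as the primary OCA-related event, and the hepatic decompensation events listed in 13.1.1.4. With about 25 patients per arm, one or two misattributed events are visible in a table.

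Two further points follow from the same text. The patient-year denominators in 15.4.4 keep running after study drug stops. The end of follow-up also differs between endpoints within that one section, so incidence, event-day and time-to-event results would not share a risk period.

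**Working it through.** The plan states no figure that depends on this rule. The planned size is consistent: 20 + 10 + 20 = 50 (15.2), which at 1:1 gives 25 per arm.

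**Step 1: follow one patient through the text.** A placebo patient starts commercial OCA, stops placebo and stays (8.4.1, 9.2.2). New pruritus is then collected (13.1.4.1). It was absent before the first dose, so it meets 13.1.1.3. It is tabulated by treatment group (15.4), and the only group available is placebo. The time enters the placebo patient-years (15.4.4). The censoring rules apply only to patients who never reported the event, so this pruritus also counts as a time-to-event occurrence.

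**Step 2: effect on incidence.** Let pP and pO be the true risks on placebo and OCA, and x = k/25 the proportion of placebo patients who switch. If a switcher carries the OCA risk:

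- observed placebo risk = (1 − x)·pP + x·pO
- observed difference = (1 − x)·(pO − pP)

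The protocol gives neither event rates nor switch rates, so the risks and k below are assumptions.

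| k of 25 | x | share kept | pO 60%, pP 30% (true 30 points) | pO 40%, pP 20% (true 20 points) |
|---|---|---|---|---|
| 0 | 0 | 1.00 | 30.0 | 20.0 |
| 1 | 0.04 | 0.96 | 28.8 | 19.2 |
| 2 | 0.08 | 0.92 | 27.6 | 18.4 |
| 3 | 0.12 | 0.88 | 26.4 | 17.6 |
| 5 | 0.20 | 0.80 | 24.0 | 16.0 |

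An extreme bound lets every switcher have the event, so observed placebo risk = (1 − x)·pP + x. With k = 5 this is 0.8 × 0.30 + 0.2 = 0.44, a difference of 16 points; or 0.8 × 0.20 + 0.2 = 0.36, a difference of 4 points.

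**Step 3: effect on event-day rates.** The same form holds with x replaced by t, the share of placebo patient-time spent on commercial OCA. The observed rate difference is (1 − t) times the true one.

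**Step 4: time off all OCA in the OCA arm.** A patient who stops at Week 12 contributes 12/48 = 25% on-drug time if followed to Week 48. If followed for the roughly 3 years in 7.1.3, taken as 156 weeks, the share is 12/156 = 7.7%. Event days that occur only on drug are then spread over a longer denominator, which lowers the event-day rate. Patient incidence behaves differently. Its denominator is a fixed count of patients, so longer follow-up can only add patients with events. It cannot fall and may rise.

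**The case against.** The strongest reply is that on-treatment windows normally belong in the SAP, which is not shown here, and that a generic TEAE definition in a protocol is common. That would settle the matter if the protocol were merely silent. It is not: it fixes an open-ended definition, an explicit patient-year formula and explicit censoring dates, and a SAP that cut at commercial OCA would be changing them.

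Other parts of the reply carry weight:

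- No sentence says that switchers are analysed in their original arm. This is an inference from two treatment groups and no reassignment rule.
- Section 13.1.1.1 ties an adverse event to temporal association with investigational product, and Table 9 asks for a reasonable temporal sequence. The related-event table may therefore filter some late or commercial-OCA events. The all-causality TEAE table has no such filter.
- Suspected drug-related hepatic injury goes to blinded adjudication (15.9), but that does not decide which arm or period an event belongs to.
- Section 7.1.3 plans a separate lock for the 48-week period, so the full 3 years need not enter the main comparison.
- Open-ended capture has a purpose, because 13.1.8 notes that liver injury may appear after a drug is stopped.

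A reader might infer that commercial-OCA time and off-drug time both hide harm. Step 4 shows that this fails for patient incidence. A reader might also take the 30 days in 13.1.7 as a ready-made TEAE window, but those 30 days run from leaving the study, not from the last dose.

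**Conclusion.** The point holds as a fault in what the protocol fixes. Applied literally, and with no reassignment rule, events and time on commercial OCA in placebo patients are credited to placebo, which pulls the arms together. Under the assumption that switchers carry the OCA risk, 1 to 5 of 25 switching leaves 96% to 80% of the true difference. The number who will switch is unknown, and with none this bias is zero.

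Off-drug time dilutes only the pruritus and fatigue event-day rates. The inconsistent censoring in 15.4.4 stands regardless of how many switch.

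Severity is moderate. Section 15.4 makes the safety comparison descriptive, so the damage is a blurred contrast and not a type I error. Because collection continues, the data needed to separate the periods should exist. A must-fix reading would need evidence of substantial switching, which the protocol does not give.

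**What to change.** In 13.1.1.3 and 15.4, end the main TEAE window at the earlier of (a) the first commercial OCA dose and (b) a prespecified interval after the last dose of investigational product. The sponsor should set and justify the length of (b) before unblinding, since 13.1.7 does not supply it. Apply the same end date to the pruritus and fatigue patient-years and to all six time-to-event censoring rules in 15.4.4.

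Show later events separately, split by commercial OCA use. Keep an all-follow-up table by randomized group, including deaths and hepatic events, because liver injury may appear after stopping. State in 15.1 how switchers are assigned to a group.

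The cost is wording in the protocol and SAP plus supplementary tables. Start of commercial OCA should be available from the concomitant medication record (9.2), and visits and treatment do not change. The downside is that late-onset events leave the main TEAE table and must be read in the supplementary ones.

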The analysis of time to first onset of treatment-emergent pruritus AE, time to onset of the first moderate or severe treatment-emergent pruritus, and onset of the first severe treatment-emergent pruritus will include the number of patients with pruritus (first onset, first moderate or severe, first severe), the number of patients without pruritus (censored), and the minimum and maximum times in days. KM estimates will be calculated by treatment group. The tabulation will include the KM estimate methodology using 25th, 50th (median), and 75th percentiles of the medians and corresponding with associated 2-sided 95% confidence intervals (CIs), if the medians can be estimated as well as percentage of censored observations.

Fatigue: Treatment-emergent fatigue is defined as any PT which includes “Fatigue.” New or worsened treatment-emergent fatigue is defined as follows:

- Any mild, moderate, or severe treatment-emergent fatigue events in patients with no fatigue at Baseline, or
- Worsening of the severity of the Baseline condition in patients with fatigue at Baseline.

Baseline fatigue is defined as the Investigator’s rating of severity as collected on the PBC Disease History eCRF. Patients whose Baseline severity is severe will be counted as worsening if an AE of fatigue with severe is recorded.

An analysis of treatment-emergent fatigue event days per patient years on study will be performed. The days at each severity grade, including the total days of event, the total patient years on study, and the event days per patient year on study at each severity grade, including the total, will be summarized. Each individual patient year on study will be derived as the last known date during the study minus the first dose date plus 1 divided by 365.25 days/year.

In order to explore the relationship between fatigue and the investigational product, the following time-to-event analyses will be performed:

- Time to first onset of treatment-emergent fatigue
 - The time to the start of the first episode will be calculated by date of onset of first episode – date of first dose of investigational product + 1.
 - Patients who never reported an AE of fatigue will be censored at the date of last contact.
- Time to onset of the first moderate or severe treatment-emergent fatigue

- The time to the start of the first moderate or severe fatigue will be calculated by date of onset of the first moderate or severe fatigue – date of first dose of investigational product +1.

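### Treatment-emergent events and pruritus/fatigue rates have no end-of-exposure rule, so off-drug time and events on commercial OCA count in the assigned arm

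*Protocol*

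**What the plan says.** **Window.** Section 13.1.1.3 covers events that first appear once dosing has begun, together with "any event already present that worsens in either intensity or frequency following exposure to the investigational product". It gives a start and no end. Under Section 13.1.4.1, "AE data will be collected from the time that signed informed consent is obtained until the patient fully completes her/his study participation".

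**Follow-up after stopping.** Section 8.4 expects patients who discontinue investigational product to remain until the study ends. Section 8.4.1 lists starting commercial OCA as a reason to stop investigational product while staying in the study. Section 9.2.2 adds: "Patients who initiate with commercial OCA therapy must discontinue investigational product and are expected to continue through the end of the study". Table 6, note b, classes these patients under treatment discontinuation, and Section 13.1.6 requires their serious events to be reported. Section 7.1.3 puts double-blind treatment at 48 weeks or more, running to about 3 years.

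**Tabulation.** The Safety Population is everyone with at least one dose (Section 15.1). Section 15.4 tabulates events by treatment group. No rule moves a patient who starts commercial OCA out of the assigned group.

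**Rates.** For pruritus event days, Section 15.4.4 states: "Each individual patient year on study will be derived as the last known date during the study minus the first dose date plus 1". The result is then converted from days to years. For fatigue: "An analysis of treatment-emergent fatigue event days per patient years on study will be performed", with the same derivation.

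**Censoring.** For first pruritus: "Patients who never reported an AE of pruritus will be censored at the date of last contact". For moderate or severe pruritus: "Patients who never reported a moderate or severe AE of pruritus will be censored at the date of completion or discontinuation"; severe pruritus follows the same rule. All three fatigue analyses censor at last contact.

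**The concern.** Safety and tolerability against placebo is one of the two primary objectives (Section 6.1), and pruritus is the main adverse event that the protocol attributes to OCA (Section 5.6). With no end to exposure, three things happen.

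- A placebo patient who starts commercial OCA and then itches is a placebo case. The control arm is contaminated by the study drug itself.
- Off-drug time in the OCA arm enters the denominator of the event-day rates and lowers them.
- If the discontinuation named in the pruritus censoring rule is of drug, events and non-events follow different clocks.

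Commercial use is foreseeable. Section 5.1 records approvals in several regions, Section 5.4.2 says that US labelling covers moderate and severe impairment, and four separate places in the protocol provide for it. With about 25 patients per arm, a few misplaced events would visibly change a table.

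**Working it through.** The protocol gives no figure for the size of this effect, so there is none to reproduce. Its relevant inputs are about 50 patients at 1:1 (25 per arm) and a 15% discontinuation rate, which Section 15.2 states for the OCA group in the PK sample size. At 15%, 25 × 0.15 = 3.75 patients per arm add off-drug time. Stopping times, event rates and commercial-OCA uptake are my assumptions.

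**1. Denominator.** Assume stopping at month 3 of 2 years. On-drug share of on-study time = [(1 − d) × 2 + d × 0.25] / 2, where d is the proportion stopping.

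- d = 15%: (1.70 + 0.0375) / 2 = 0.869, so 13% is off drug.
- d = 20%: (1.60 + 0.05) / 2 = 0.825, so about 17% is off drug.
- d = 30%: (1.40 + 0.075) / 2 = 0.7375, so 26% is off drug.

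The on-drug event-day rate is understated by these percentages if no event days fall off drug, and by less if some do.

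**2. Incidence.** Assume pruritus in 20% on placebo and 50% on OCA, with a share p of placebo patients starting commercial OCA and then having the OCA incidence. Placebo-arm incidence = 0.20(1 − p) + 0.50p, so the risk difference is 0.30 − 0.30p.

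- p = 10%: 27 points.
- p = 20%: 24 points.
- p = 30%: 21 points.

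Starting commercial OCA requires stopping investigational product. If 15% also holds in the placebo arm, p cannot exceed 15%, which gives 0.30 − 0.045 = 25.5 points. The larger losses need more stopping.

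**3. Rate ratio.** Assume a true ratio of 2.0, stopping at Week 24, and OCA-arm stoppers returning to background. Off-drug share f = d × (follow-up − 24) / follow-up. Observed ratio = [1 + (1 − f)(2 − 1)] / [1 + c·f·(2 − 1)], where c is the share of placebo off-drug time spent on commercial OCA.

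| Stopping | Follow-up | f | Ratio, c = 0 | Ratio, c = 1 |
|---|---|---|---|---|
| 15% | 48 weeks | 0.075 | 1.93 | 1.79 |
| 15% | 156 weeks | 0.127 | 1.87 | 1.66 |
| 30% | 48 weeks | 0.150 | 1.85 | 1.61 |
| 30% | 156 weeks | 0.254 | 1.75 | 1.39 |
| 50% | 48 weeks | 0.250 | 1.75 | 1.40 |
| 50% | 156 weeks | 0.423 | 1.58 | 1.11 |

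The movement is always towards 1. It is small at 15% without commercial OCA and grows with stopping, follow-up and uptake.

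**4. Censoring.** Of the six time-to-event analyses, four end at last contact. The two for moderate-or-severe and severe pruritus end at completion or discontinuation, without saying of what. If drug is meant, take two patients who stop at month 3. One has severe pruritus at month 9 and is an event at month 9; the other never does and leaves the risk set at month 3. The later risk set then lacks event-free stoppers, and the Kaplan-Meier incidence is biased upwards. If study is meant, the rule is close to last contact and only the wording differs.

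**The case against.** **An end to the window is usual SAP material.** This is partly right: a lag after last dose is often set there. But the safety sections themselves fix the on-study denominator and the censoring dates, and they do not defer these to the SAP as Sections 15.3 and 15.6 do for PK and additional efficacy. An open-ended definition combined with those rules is a choice that the protocol has made.

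**Counting all on-study events is legitimate.** This stands. It is a treatment-policy summary, and it matters for the liver. Tables 3 to 5 tie interruption and discontinuation to hepatic worsening, and Section 13.1.8 warns that drug-induced injury can appear or progress after the drug is stopped. A reader might infer that the current rule understates hepatic events on OCA. The documents do not support that: an on-treatment cut could itself remove late decompensations from the OCA count. So the on-study table should not be displaced.

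**The size is easily overstated.** This also stands. A reader might give placebo switchers 1 − 0.8 × 0.5 = 60% pruritus and reach a risk difference of 22 points (26 to 18), but the assumed 50% on OCA already contains the background. A reader might also take the 26% denominator effect as typical, but it needs 30% stopping, twice the only rate in the protocol. Off-drug time dilutes the event-day rates; it cannot remove a patient already counted in the OCA incidence tables.

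**Harm is limited.** Safety is descriptive (Section 15.4), so no error rate is inflated, and concomitant medication and end-of-treatment data would allow a later on-treatment table. That table would, however, be defined after the fact.

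**Conclusion.** The point holds, at modest size. The TEAE window has no end, the pruritus and fatigue rates use on-study time, and patients on commercial OCA stay in their assigned group. For pruritus and fatigue this pulls the arms together. At 15% stopping, about 13% of the denominator is off drug (stop at month 3 of 2 years). With assumed incidences of 20% and 50%, the risk difference loses 3 to 9 of 30 points for 10% to 30% commercial-OCA uptake, and the upper part of that range requires more than 15% of placebo patients to stop. For hepatic events, the misattribution is real but the net direction is unknown.

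The pruritus censoring is inconsistent as written. Whether it also biases the curves depends on what discontinuation means there, which the protocol does not say.

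A reader might also take the 30 days in Section 13.1.7 as the protocol's own treatment-emergent window. It is not: it runs from leaving the study and governs reporting of serious events.

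**What to change.** - Keep the all-on-study tables of TEAEs and events of special interest, and flag in them any event after the start of commercial OCA.
- Beside them, add on-treatment tables for TEAEs, events of special interest, pruritus and fatigue, with event-day rates for pruritus and fatigue. The period and its patient-years run from first dose to last dose plus a prespecified lag, or to the start of commercial OCA, whichever comes first. State and justify the lag, since the protocol supplies none.
- In every pruritus and fatigue time-to-event analysis, apply the same end date to events and to censoring, and replace the undefined completion-or-discontinuation date with a defined one.

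The cost is a definition change and a second set of adverse event tables. No new data are needed and patient management does not change. Late off-drug events drop out of the on-treatment tables, which is why both sets must be shown.
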